25.4 Statement of Investigator

Prior to initiation of the study, all Investigators who will participate in the investigation must sign the Statement of Investigator. No Investigators will be added to the investigation until they have signed the agreement.

25.5 Financial Disclosure by Clinical Investigators

Each Investigator must disclose certain financial arrangements that may exist between the Investigator and Smith & Nephew. This information will be collected and maintained confidentially at Smith & Nephew and will be available for review upon request. This information must be updated promptly by the Investigator and submitted to the Sponsor if any changes occur through the duration of the study and for one year following the completion of the study.

26.0 Insurance

Public/Products liability insurance has been purchased by Smith & Nephew worldwide and incorporates coverage for personal injury in respect of clinical studies.

27.0 Other

Before the start of the study the Principal Investigator will take responsibility for informing the National Health Research Ethics Council, the South African National Clinical Trials register (SANCTR) and/or regulatory authority (if applicable) of research to take place.

## 1. List of Abbreviations

Abbreviation	Definition
AE	Adverse Event(s)
ANOVA	Analysis of Variance
HHS	Harris Hip Score
HOOS	Hip Disability and Osteoarthritic Outcome Score
ITT	Intention to Treat Population
LOCF	Last Observation Carried Forward
N (or n)	Total Sample Size (or subgroup sample size)
PP	Per-protocol Population
SAE	Serious Adverse Event(s)
SAP	Statistical Analysis Plan
TFL	Tables, Figures and Listing

Statistical Analysis Plan	
A Consecutive Series Pilot Study Evaluating the Safety and Effectiveness of a New Hard-on-Hard Total Hip Replacement System in Patients with Non-inflammatory Arthritis with a Standard THA Metal Ion Control Group	Number: 2011-ODHH166 ST: 1040
	Version: V1.0 26-Nov-2018
	Page: 5 of 13

## 2. Introduction

The following Statistical Analysis Plan (SAP) details the statistical considerations, including the data analysis methods, for the Study Protocol 2011-ODHH166. Related documents to this SAP are the Study Protocol, Case Report Form (CRF), and Tables, Figures and Listings (TFL) Templates Shells.

## 3. Study Design

Prospective, consecutive series, non-randomised, multicenter study evaluating the Safety and Effectiveness of a New Hard-on-Hard Total Hip Replacement System in Patients with Non-inflammatory Arthritis with a Standard THA Metal Ion Control Group.

### Schedule of Assessments

Schedule	Preop	Op	DC	3 mo $\pm$ 4 wks	6 mo $\pm$ 4 wks	1 yr $\pm$ 4 wks	2 yr $\pm$ 6 wks	5yr -2 wks+ 180 days	6yr $\pm$ 90 days	7yr $\pm$ 90 days	8yr $\pm$ 90 days	9yr $\pm$ 90 days	10yr $\pm$ 180 days	Unscheduled
Days	-	-	-	64-120	155-211	338-394	689-773	1812-2006	2101-2281	2466-2646	2831-3019	3196-3376	3471-3831	-
Inclusion/Exclusion	✓	-	-	-	-	-	-	✓	-	-	-	-	-	-
Informed Consent	✓	-	-	-	-	-	-	✓	-	-	-	-	-	-
Demographics/Med History	✓	-	-	-	-	-	-	-	-	-	-	-	-	-
Clinical Evaluation (HHS)	✓ a	-	-	✓ a	✓ a	✓ a	✓ a	✓	-	✓	-	-	✓	✓ a
Radiography	✓ a	-	✓ a	✓ a	✓ a	✓ a	✓ a	✓		✓			✓	✓
Metal Ion Testing (Whole Blood)	✓	-	-	✓	✓	✓	✓	✓	-	✓	-	-	✓	✓
HOOS Subject Questionnaire	✓ a	-	-	✓ a	✓ a	✓ a	✓ a	✓	-	✓	-	-	✓	✓ a
Adverse Events	-	✓	✓	✓	✓	✓	✓	✓	✓	✓	✓	✓	✓	✓
End of Study	-	-	-	-	-	-	-	-	-	-	-	-	✓ c	-
Retrospective Demographics/Med History Data Collection b	✓	✓	✓	✓	✓	✓	✓	-	-	-	-	-	-	-
Retrospective Clinical Evaluation (HHS) b	✓			✓	✓	✓	✓							
Retrospective HOOS b	✓			✓	✓	✓	✓							
Retrospective Adverse Event Data Collection b	✓	✓	✓	✓	✓	✓	✓	-	-	-	-	-	-	-
Retrospective Radiography Data Collection b	✓	✓	✓	✓	✓	✓	✓	-	-	-	-	-	-	-

a - For Investigational subjects only

b - Control subjects only

c - An end of study form will be completed for all subjects at the 10 year visit if not completed prior

Statistical Analysis Plan	
A Consecutive Series Pilot Study Evaluating the Safety and Effectiveness of a New Hard-on-Hard Total Hip Replacement System in Patients with Non-inflammatory Arthritis with a Standard THA Metal Ion Control Group	Number: 2011-ODHH166
	ST: 1040
	Version: V1.0 26-Nov-2018
	Page: 6 of 13

#### 4. Study Endpoints

##### 4.1 Primary Endpoints

The primary endpoints for this study are:

- Device-Related Revisions
- Adverse Events
- Metal Ion levels in whole blood [Cobalt (Cr), Chromium (Cr), Nickle (Ni), Titanium (Ti), Zirconium (Zr), Niobium (Nb), Molybdenum (Mo), Vanadium (V) and Aluminium (Al)].

##### 4.2 Secondary Endpoints

The secondary endpoints for this study are:

- The Harris Hip Score (HHS)
- Hip Disability and Osteoarthritis Outcome Scores (HOOS)
- Radiographic Success, including the assessment of bone loss, radiolucencies, subsidence, and heterotopic ossification as compared to the preoperative radiograph.
- Health Economic Data
  - Surgical blood loss
  - Length of hospital stay
  - Operative time
  - Re-hospitalizations

Statistical Analysis Plan	
A Consecutive Series Pilot Study Evaluating the Safety and Effectiveness of a New Hard-on-Hard Total Hip Replacement System in Patients with Non-inflammatory Arthritis with a Standard THA Metal Ion Control Group	Number: 2011-ODHH166
	ST: 1040
	Version: V1.0 26-Nov-2018
	Page: 7 of 13

## 5. Statistical Considerations

### 5.1 Determination of Sample Size

A total of 25 subjects were enrolled in the study (20: ODH-ODH and 5 controls). All patients completing the 2 year primary follow up were invited to participate in the extension phase of the study. No justification for the sample size was provided.

### 5.2 Randomisation

No randomization took place for this study. Instead Subjects who refuse ODH-ODH enrollment were asked to participate in the control group.

### 5.3 Interim Analysis

Interim analyses will be conducted post-operatively after all subjects have completed 5 year and 7 years visits. The focus of these analyses will be on safety and efficacy.

## 6. Statistical Analysis

### 6.1 General

Smith & Nephew's Global Biostatistics group will conduct the statistical analysis for this study. Unless otherwise stated, all statistical significance tests conducted will be two-sided, performed at the 5% significance level. Resulting p-values will be quoted and 95% two-sided confidence intervals will be generated where appropriate. All p-values will be rounded to three decimal places, p-values less than 0.001 will be presented as '<0.001' in all tables.

Where data summaries are specified, categorical and ordinal variables will be summarized with frequencies and percentages. Continuous variables will be summarized with the following summary statistics: number of observations, mean, median, standard deviation, minimum and maximum values. All analyses will be performed in SAS 9.4 (or later).

### 6.2 Analysis Populations

The following analysis populations will be used for this study:

Statistical Analysis Plan	
A Consecutive Series Pilot Study Evaluating the Safety and Effectiveness of a New Hard-on-Hard Total Hip Replacement System in Patients with Non-inflammatory Arthritis with a Standard THA Metal Ion Control Group	Number: 2011-ODHH166
	ST: 1040
	Version: V1.0 26-Nov-2018
	Page: 8 of 13

- **Safety Population (SAF):** Including all subjects who have enrolled in the study and received the study treatment. This population will be used for analysis of safety data including the primary endpoints.
- **Intention to treat population (ITT):** following Intention to Treat principle including all subjects enrolled into the study, this does not include those who only provide retrospective data. This population will be used for the primary analysis of secondary endpoints.
- **Per-Protocol Population (PP):** including all subjects in the ITT, who have no significant protocol deviations and who meet the inclusion/exclusion criteria. This population will be used as a secondary analysis of secondary endpoints.

#### 6.3 Handling of Missing, Incomplete and Repeat Data

- **Revision data** - If a subject has a revision at any point during the study, for purposes of calculating the revision rate by a particular visit then the fact that a revision has occurred will be carried forward to all the following visits.
- **HHS/ HOOS** – If any individual HHS/ HOOS responses are missing at a post-baseline visit then the data will be input from the previous assessment using the Last Observation Carried Forward (LOCF) method. If baseline is the only previous data point then no implementation methods should be used, baseline data should not be carried forward. If all HHS/ HOOS responses are missing at a post-baseline visit (including if a subject has discontinued from the study) then all missing dimension scores should be carried forward using the LOCF method as above, with no carrying forward of baseline values.

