18.0 Device Failure leading to revision

In the short term, THA failure can occur due to infection, dislocation, instability, and/or subject experiencing severe pain due to various causes. Reduced mobility alone, is typically not a predominant factor in prompting revision surgery. In the longer-term, aseptic loosening and/or severe pain may become a determining factor as to whether to proceed with device revision. Reasons for removal are not limited to these circumstances alone.

The Sponsor should be notified immediately when a revision is planned. The Sponsor or its designee will provide an explant retrieval kit and the site will return any revised components for retrieval analysis according to provided instructions. Any explanted devices must be logged on the device accountability log when explanted and shipped to the Sponsor or its designee. Blood will be collected for metal ion analysis and radiographs taken prior to the revision procedure as per an unscheduled visit on the study visit schedule. Patients who have undergone revision surgery will be withdrawn from the study and no additional follow-up visits will occur.

Explanted components are to be sterilized by steam autoclave or other appropriate sterilization method according to the Institution's standard sterilization procedures. Only properly packaged explants should be shipped, and the Sponsor notified before any shipment. If possible, the Sponsor will collect histological (bony in-growth quality, bone quality, response to potential wear debris, etc.) and metallurgical (metal wear, deformation, cracking, corrosion, etc.) information from explants, and this information will be reported in annual safety reports. For all explants, the Investigator must record and forward a description of intra-operative findings including: 1) presence of wear debris, 2) what types of components are being replaced, 3) and intraoperative findings relating to the device failure. It should be noted that the Sponsor is not always able to retrieve known explants.

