22.3 Statistical Analysis

22.3.1 Analysis of Population

2 years Primary Study Analysis

The primary analysis will be comprised of all patients who have completed the 6 month post-operative follow-up visit. Twenty-Five patients who have completed the 6 month visit are needed to complete the primary interim analysis and the metal ion analysis will compare to control subjects. A final analysis which will include efficacy assessments will be completed at the 2 year time point. All subjects who do not complete the study, for reasons other than device failure, will be described in the final analysis.

The control subjects will ONLY be asked for blood samples and no other study assessments will be required. Therefore, they will not be included in the over-all analysis. The metal ion results of the five control subjects will be compared to those

of the 20 ODH subjects in order to validate the metal ion levels in the ODH population.

5, 7 and 10 year Study Analyses

The extension study will be comprised of all subjects who have completed the 5 year, 7 year and 10 year post-operative follow-up visits. The analyses will include the descriptive statistics in both safety and efficacy variables. All the data collected during the study will be presented as tables or listing.

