### 6.10 Analysis of Secondary Endpoint(s)

All secondary endpoints are assessed primarily using the ITT population and the PP population will be used for a secondary analysis.

The analysis of HHS and HOOS will be performed on observed data as well as with LOCF imputed data.

Statistical Analysis Plan	
A Consecutive Series Pilot Study Evaluating the Safety and Effectiveness of a New Hard-on-Hard Total Hip Replacement System in Patients with Non-inflammatory Arthritis with a Standard THA Metal Ion Control Group	Number: 2011-ODHH166
	ST: 1040
	Version: V1.0 26-Nov-2018
	Page: 12 of 13

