#### 6.10.1 The Harris Hip Score (HHS)

Where HHS data has been collected it will be summarised using descriptive statistics at baseline, 6-months, 2 years, 5 years, 7 years and 10 years visits by treatment and overall.

The change from baseline in HHS score as derived in section 6.4 will also be summarised at the same study visits by treatment and overall.

Paired t-tests will be used to test for a difference in the change from baseline HHS score for each treatment separately from baseline to 5-years, 7-years and 10-years. The differences will be presented along with the associated 95% confidence intervals. If the assumptions of the t-test is violated then the Wilcoxon signed rank test will be used instead with Hodges-Lehmann estimates of the median difference and 95% confidence interval reported.

A sensitivity analysis will be carried out in the same way as described above however using the data as it is recorded without LOCF methods applied.

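### LOCF with no time limit, continuing past discontinuation and so past revision, by implication leads the 5-, 7- and 10-year HHS and HOOS analyses

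*SAP*

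**What the plan says.** SAP 6.3 has two carry-forward rules for HHS and HOOS.

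- Single items: "If any individual HHS/ HOOS responses are missing at a post-baseline visit then the data will be input from the previous assessment".
- Wholly missing visits: "including if a subject has discontinued from the study) then all missing dimension scores should be carried forward using the LOCF method".

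The only limit on either rule is that baseline is never carried. No maximum interval is set and revision is not an exception.

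Protocol 18.0 deals with revision: "Patients who have undergone revision surgery will be withdrawn from the study and no additional follow-up visits will occur". A revised patient is therefore a discontinued one for the purposes of SAP 6.3.

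On which analysis leads, SAP 6.10 states: "The analysis of HHS and HOOS will be performed on observed data as well as with LOCF imputed data". It does not rank the two. SAP 6.10.1 then describes summaries and paired tests against baseline at 5, 7 and 10 years, and adds a sensitivity analysis "using the data as it is recorded without LOCF methods applied". SAP 6.10.2 does the same for HOOS.

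On who is analysed, the SAP 6.2 ITT set is described as "including all subjects enrolled into the study, this does not include those who only provide retrospective data". Protocol 22.3.1 says of the 5-, 7- and 10-year analyses: "The extension study will be comprised of all subjects who have completed the 5 year, 7 year and 10 year post-operative follow-up visits".

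**The concern.** The extension exists to assess long-term safety and efficacy (protocol 2.0). A 10-year mean that contains scores recorded years earlier, or on a hip since revised, is not a 10-year result for those subjects. SAP 6.3 also carries revision status to all later visits, so one subject can be counted as revised at a visit while contributing function measured before the revision.

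The direction of bias is not fixed. A good earlier score can hide later decline, and a score from early recovery or from a failing hip can understate function. The interval also treats each carried score as if it had been measured at that visit.

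The groups are small. One carried score has a weight of 1/20 in the ODH group and 1/5 in the control group.

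**Working it through.** **Which analysis leads.** SAP 6.10 lists both without ranking. In 6.10.1 and 6.10.2 the run without LOCF is labelled a sensitivity analysis of what precedes it. What precedes it must then be the LOCF version. This is an inference, since the SAP never calls LOCF primary. It is firmest for the paired tests, because the paragraphs on summaries open by limiting themselves to data that were collected.

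**Which enrolment defines ITT.** SAP 5.1 uses the word for the original cohort: "A total of 25 subjects were enrolled in the study". SAP 6.2, however, excludes subjects who give only retrospective data, which fits enrolment in the extension. The two readings give different carry distances.

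**Age of a carried score** (target visit minus last scored visit, scheduled visits only). HHS and HOOS are scheduled at 3 and 6 months and at 1, 2, 5, 7 and 10 years.

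| Reading of ITT | Last score | At 5 y | At 7 y | At 10 y |
|---|---|---|---|---|
| Extension enrolment | 5 y | – | 7 − 5 = 2 | 10 − 5 = 5 |
| Extension enrolment | 7 y | – | – | 10 − 7 = 3 |
| Original enrolment, not in extension | 2 y | 5 − 2 = 3 | 7 − 2 = 5 | 10 − 2 = 8 |

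The first row assumes that a 5-year score was recorded; the schedule places extension consent at that visit.

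Two other sources could supply a later score. Protocol 15.0 requires a final evaluation for subjects who do not finish, without listing its content. The unscheduled column of the schedule ticks HHS and HOOS for investigational subjects, and protocol 18.0 refers to that visit before a revision, although it names only blood and radiographs. SAP 6.3 does not say whether such scores count as the previous assessment.

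**Interval width.** The documents give no dropout, revision count or SD, so the counts below are assumed. The ODH group has n = 20. The 95% CI half-width in SD units is t(0.975, n−1)/√n.

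| Carried | Observed n | Observed half-width | LOCF half-width (n = 20) | Ratio at equal SD | LOCF CI narrower by |
|---|---|---|---|---|---|
| 2 | 18 | 0.4973 | 0.4680 | 0.941 | 6% |
| 6 | 14 | 0.5774 | 0.4680 | 0.811 | 19% |
| 10 | 10 | 0.7154 | 0.4680 | 0.654 | 35% |

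Equal SDs are a condition of this result. The LOCF interval becomes the wider one once carried scores raise the SD by more than the inverse ratio: 1.06, 1.23 or 1.53.

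**An example in the other direction** (all values assumed). Take 18 observed changes with mean 45 and SD 10, and two carried changes of 15.

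- LOCF mean = (18×45 + 2×15)/20 = 42, against 45 for completers.
- LOCF SD = √[(17×100 + 18×(45−42)² + 2×(15−42)²)/19] = √(3320/19) = 13.22.
- Half-widths: 0.4680×13.22 = 6.19 against 0.4973×10 = 4.97. The ratio is 1.244, so the LOCF CI is 24% wider.

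**Shift in the mean** is (k/n) × (carried score − true score at the visit). For a gap of 20 points (assumed), two of 20 ODH subjects move the mean by 2/20 × 20 = 2 points. One of five controls moves it by 1/5 × 20 = 4 points.

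**The case against.** Four points deserve weight.

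- **Both analyses are already planned.** SAP 6.10 names observed data first, and readers will see both. This stands, and it makes the change cheap. It does not settle which result is reported as the main one, and the sensitivity label points to LOCF.
- **Observed-only analysis has its own bias.** It drops revised patients. In the example above, moving from LOCF to completers raises the mean from 42 to 45, so the remedy can favour the device. It also rests on an assumption about missing scores that cannot be tested. This stands as a downside to report. It does not justify presenting a pre-revision score as 10-year function.
- **Carried scores may be recent.** A final evaluation or an unscheduled visit could supply one. This is possible, but the SAP is silent, so the ages in the table hold for scheduled visits only.
- **The protocol wording is loose.** Protocol 22.3.1 can mean completers of each visit or of all three, and read literally it cannot define a 5-year interim population. Protocol 22.3.4 plans an accountability table and neither specifies nor forbids imputation. A reader might infer that LOCF breaches the protocol, but the text does not go that far. On either reading, however, LOCF adds subjects who did not attend, so the two documents need reconciling.

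**Conclusion.** The concern holds. As written, SAP 6.3 with protocol 18.0 lets pre-revision and years-old scores enter the 5-, 7- and 10-year HHS and HOOS estimates, and SAP 6.10.1 and 6.10.2 by implication put that version first. On scheduled visits, the carried score is 2 years old at 7 years and 3 or 5 at 10 years. Under original enrolment, a carried 2-year score is 3, 5 or 8 years old at 5, 7 or 10 years. The narrowing of 6%, 19% or 35% rests on assumed counts and equal SDs.

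Stronger readings are tempting but unsupported:

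- that LOCF flatters the device or always narrows the interval (the example shows a lower mean and a wider CI);
- that a score used at 10 years is usually 5 years old (a 7-year score is 3 years old, and no dropout data are given);
- that the study's main conclusions are at risk. HHS and HOOS are secondary and have no success threshold, and the primary safety endpoints do not use this rule. Only the reported long-term functional estimate is affected.

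**What to change.** - **SAP 6.10, 6.10.1 and 6.10.2:** make the analysis of visits actually attended the lead, with whole-visit LOCF at most a sensitivity analysis.
- **SAP 6.3:** do not carry whole-visit scores past revision, discontinuation or non-entry to the extension. Say whether final-evaluation and unscheduled scores count as previous assessments. Handle a single missing item at an attended visit separately, under the scoring instructions that 6.4 already cites.
- **SAP 6.2:** state which enrolment defines ITT, and reconcile it with protocol 22.3.1.
- **Reporting:** beside each late-visit mean, show the number observed and the cumulative number revised. List the last pre-revision score of revised subjects where one was recorded.

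The cost is mostly wording. Both analyses are planned, SAP 6.1 already requires the number of observations, and 6.3 already carries revision status to later visits. The new work is the item rule and one short listing. The price is a smaller n and usually wider intervals at late visits. A total may still be lost if the scoring instructions, which are not in the documents, do not allow a missing item. Because an observed-only mean omits revised patients and may favour the device, the revision count and the LOCF sensitivity result must be reported with it.

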#### 6.4 Derived Data

##### Analysis Populations

- Indicator for inclusion in SAF
- Indicator for inclusion in the ITT

Statistical Analysis Plan	
A Consecutive Series Pilot Study Evaluating the Safety and Effectiveness of a New Hard-on-Hard Total Hip Replacement System in Patients with Non-inflammatory Arthritis with a Standard THA Metal Ion Control Group	Number: 2011-ODHH166
	ST: 1040
	Version: V1.0 26-Nov-2018
	Page: 9 of 13

- Indicator for inclusion in the PP

#### Demographics, Baseline Data and Disposition Data

- Age = (Date of preop visit – date of birth) /365.25  
Note: Round down to the nearest whole number.
- Body Mass Index (BMI)[kg/m^2] = weight [kg] \* (height [cm]/100)
- Baseline is considered as the Pre-Op visit.
- Indicator for bilateral subject.

#### Revision Data

- Any subject classified as lost-to-follow-up, deceased or withdrawn will be censored in the survival analysis on the date which it occurs. If a device-related revision occurs this will be considered a device failure. If none of the above occur before the end of the study the subject will be censored on end of study visit/ date of interim analysis.

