14.0 Post-operative Procedures

Subjects will be seen post-operatively at the 3 month, 6 month, 1, 2, 5, 7 and 10 year intervals, post-surgery. At the discretion of the Sponsor, additional unscheduled follow-up visits may be performed. Information regarding interval specific study events may be found in the Study Events Schedule.

Post-operative procedures include:

- Revision status
- Assessment of adverse events
- Collection of whole blood samples for metal ion analysis at the 3 month, 6 month, 1, 2, 5, 7 and 10 year intervals.
- Telephonic assessment of adverse events at 6, 8 and 9 year intervals.
- A clinical evaluation will be completed by the Investigator for purposes of completing the HHS for investigational subjects at the 3 month, 6 month, 1 and 2 year intervals. Any HHS data available for control subjects will be collected retrospectively up until 2 years post-op. From the 5 year interval onwards (5,7 and 10 year intervals) HHS will be collected prospectively for all subjects.
- AP and lateral radiographs will be obtained. Copies will be provided to the Sponsor for the purpose of obtaining independent radiographic analysis for investigational subjects. Any radiographic data available for control subjects will be collected retrospectively up until 2 years post-op. From the 5 year interval onwards all

radiographic data will be collected prospectively.

- Completion of HOOS subject questionnaire for investigational subjects at the 3 month, 6 month, 1 and 2 year intervals Any HOOS data available for control subjects will be collected retrospectively up until 2 years post-op. From the 5 year interval onwards (5,7 and 10 year intervals) HOOS will be collected prospectively for all subjects.

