15.0 Subject Withdrawals

Study participation is voluntary and subjects may withdraw at any point and for any reason during the study. A final evaluation will be completed for all subjects who do not finish the study, and the reason for the withdrawal will be documented in the source documentation and on the appropriate case report form (CRF).

The Investigator may withdraw subjects from the study for any of the following reasons:

- Serious adverse event that precludes continued participation
- Investigator's decision to withdraw subject
- Subject does not receive study device during surgery
- Subject noncompliant with visits
- Subject lost to follow-up

Reasonable efforts to keep each subject in the study should be made and these efforts should be documented by the Investigator. Although the subject is not obligated to give his/her reason(s) for withdrawing prematurely from the study follow-up procedures, the Investigator should make a reasonable effort to ascertain the reason(s), while fully respecting the subject's rights.

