16.0 Lost to Follow-up

A subject will be considered lost to follow-up if he/she does not appear for a scheduled study visit and study personnel are unable to contact the subject. Study personnel must make a reasonable effort to contact the subject and document a minimum of three contact attempts prior to declaring a subject to be lost to follow-up. Copies of all attempts to reach the subjects per regular mail or email and/or the attempts to contact the subject via other means should be documented and that documentation should be kept with the patient's CRF. An End of Study CRF should also be completed.

If a subject grants permission on the Informed Consent Form to have their family doctor/GP contacted, the study surgeon/staff may contact the subject's family doctor/GP to ascertain the overall status of the subject's health. The study surgeon/staff may only contact the subject's family doctor/GP if the subject has provided consent to do so and has NOT withdrawn consent from the study. The contact with the family doctor should be recorded in the source documentation.

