### 6.9.1 Device-Related Revisions

The Kaplan-Meier product limit survival estimates will be presented at 6-months, 2-years, 5-years, 7-years and 10-years post-op along with the associated 95% confidence intervals. The event of interest will be device-related revisions. Subjects who do not have device-related revision will be censored either at the time-point being analysed i.e. 5-years at the 5-year interim analysis etc. or at the time they discontinue from the study for

Statistical Analysis Plan	
A Consecutive Series Pilot Study Evaluating the Safety and Effectiveness of a New Hard-on-Hard Total Hip Replacement System in Patients with Non-inflammatory Arthritis with a Standard THA Metal Ion Control Group	Number: 2011-ODHH166
	ST: 1040
	Version: V1.0 26-Nov-2018
	Page: 11 of 13

any other reason i.e. lost to follow-up. This analysis will be presented by treatment (control/ R3 ODH-ODH).

The Kaplan Meier Survival plot will also be presented at 12 months both overall and by device type.

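### Lost subjects are censored when the loss occurs, not when the implant was last known to be unrevised, so Kaplan-Meier survival can be overstated and never understated

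*SAP*

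**What the plan says.** SAP 6.4 (Derived Data, Revision Data) states: "Any subject classified as lost-to-follow-up, deceased or withdrawn will be censored in the survival analysis on the date which it occurs". SAP 6.9.1 restates the rule for the Kaplan-Meier analysis: "Subjects who do not have device-related revision will be censored either at the time-point being analysed", "or at the time they discontinue from the study for" another reason, with loss to follow-up as its example. Neither section defines the date on which a loss occurs, and neither uses the last date on which the implant was known to be unrevised.

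Protocol 16.0 says how the status arises: "A subject will be considered lost to follow-up if he/she does not appear for a scheduled study visit and study personnel are unable to contact" him or her. Staff must also "document a minimum of three contact attempts prior to declaring a subject to be lost to follow-up". No time limit is set for those attempts. Protocol 15.0 lists "Subject noncompliant with visits" among the grounds on which the investigator may withdraw a subject, and asks for a final evaluation of everyone who does not finish.

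On contacts, the schedule has clinic visits at 2, 5, 7 and 10 years with nothing between years 2 and 5. Protocol 14.0 adds "Telephonic assessment of adverse events at 6, 8 and 9 year intervals".

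**The concern.** A subject contributes information about revision only up to the last contact at which implant status was established. On the protocol's own definition, loss to follow-up cannot arise at that contact. It arises later, once a visit has been missed and the attempts to reach the subject have failed. Censoring at the later date keeps the subject in the risk set, as if unrevised, over a period nobody observed. Withdrawal for visit noncompliance can have the same gap.

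At stake are the 5-, 7- and 10-year survival estimates of a new bearing in 20 hips. Any error goes one way, towards higher survival, and the confidence interval also looks tighter than the observed follow-up supports.

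**Working it through.** The plan states no survival, revision or dropout figure, so there is nothing of its own to reproduce. The check has four steps.

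**1. Length of the unobserved interval.** Inputs are the day windows in the schedule: 2 years 689–773, 5 years 1812–2006, 6 years 2101–2281, 7 years 2466–2646, 9 years 3196–3376, 10 years 3471–3831. Nominal days are 731, 1826 (= 1812 + 14), 2191, 2556, 3286 and 3651.

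- Last seen at 2 years, lost at the close of the 5-year window: 2006 − 773 = 1233 days (3.4 years) to 2006 − 689 = 1317 days (3.6 years). From the nominal day, 2006 − 731 = 1275 days (3.5 years).
- Year 5 to the 6-year call: 2191 − 1826 = 365 days (1.0 year) at the nominal date, 2281 − 1826 = 455 days (1.2 years) at the close of the window.
- Year 6 to year 7: 2646 − 2191 = 455 days. Year 9 to year 10: 3831 − 3286 = 545 days (1.5 years).

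**2. Direction.** The estimator is S(t) = Π(1 − d/n) over revision times up to t, with d revisions among n at risk. With the observed revisions fixed, later censoring leaves d alone and can only raise n, and only for revisions inside the gap. So S is equal or higher, never lower.

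**3. Size, by illustration.** Assumed: 20 ODH hips, lost subjects last seen on day 731 and classed as lost on day 2006, revisions in other subjects between day 731 and day 1826. Survival is read at 5 years (day 1826).

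| Revisions in gap | Lost | Date loss occurs | Last known status | Difference (points) |
|---|---|---|---|---|
| 0 | 2, 4 or 6 | 100% | 100% | 0 |
| 1 | 2 | 19/20 = 95.0% | 17/18 = 94.4% | 0.6 |
| 1 | 4 | 19/20 = 95.0% | 15/16 = 93.8% | 1.25 |
| 1 | 6 | 19/20 = 95.0% | 13/14 = 92.9% | 2.1 |
| 2 | 4 | 18/20 = 90.0% | 14/16 = 87.5% | 2.5 |
| 3 | 6 | 17/20 = 85.0% | 11/14 = 78.6% | 6.4 |

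For one revision and 4 lost, the log-log 95% interval (Greenwood variance) is 69.5% to 99.3% under the SAP rule and 63.2% to 99.1% under last-known-status censoring.

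Revisions outside the gap make no difference. With 4 lost, one revision on day 500 gives 95.0% both ways, and one on day 2300, read at 7 years, gives 15/16 = 93.75% both ways. In the control arm (n = 5), one revision in the gap and one lost gives 4/5 = 80% against 3/4 = 75%.

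**4. Size, on average.** Assume a constant hazard λ = −ln(S10)/10, where S10 is 10-year survival, and a fraction f of the arm unseen from year 2 to year 5. True 5-year survival is exp(−5λ). The SAP rule gives about exp(−2λ)·exp(−3λ(1 − f)). The chance of no revision among 20 hips over g years is S10^(20g/10).

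| S10 | Upward bias at 5 years, f = 10% to 30% | No revision, 3-year gap (S10^6) | No revision, 1.25-year gap (S10^2.5) |
|---|---|---|---|
| 95% | 0.15 to 0.45 points | 74% | 88% |
| 90% | 0.30 to 0.90 points | 53% | 77% |
| 80% | 0.60 to 1.8 points | 26% | 57% |

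The last two columns treat all 20 hips as observed, so they slightly understate the chance of no difference.

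**The case against.** **The SAP does not say that censoring is at declaration.** A reader might infer that it does. The SAP leaves the date of a loss undefined; the link to declaration comes from Protocol 16.0, which governs classification rather than analysis. That is fair as to wording. But on the protocol's definition the status cannot arise before the missed visit, so any natural reading puts the date after the last contact. The lack of a definition also leaves programmers to choose.

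**Survival is not necessarily overstated.** A reader might infer that it always is. With no device-related revision in the same arm during the gap, the estimate is identical and only the numbers at risk are inflated. This stands.

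**The 3.5-year gap may rarely apply.** The primary study ended at 2 years, and the schedule places extension consent and eligibility at the 5-year visit. Someone last seen at 2 years who never returns may simply have completed the primary study rather than become lost. The documents do not settle this. The case for gaps of 1 to 1.5 years is firmer.

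**Not every withdrawal is affected.** Given the final evaluation in Protocol 15.0, an active withdrawal is normally dated at a contact where implant status can be established. The exposed groups are loss to follow-up and withdrawal for visit noncompliance.

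**The effect is small against the noise.** The interval for one revision in 20 hips is about 69.5% to 99.3%, far wider than the shift, and the SAP sets no survival threshold. This bears on priority. It is no reason to keep an error of known direction that is cheap to remove.

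**Conclusion.** The point holds in a limited form. Followed as written, SAP 6.4 and 6.9.1 count unobserved time as revision-free for subjects lost to follow-up, and can do so for those withdrawn for visit noncompliance. Nothing elsewhere in the documents corrects this. Survival can be overstated, never understated, and its precision is overstated whenever the estimate moves.

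The likely shift is about 0 to 2 points. Larger values, such as 6.4 points, need several revisions and heavy loss in the same interval. All sizes rest on assumed losses, revision times and hazards, because the documents give none.

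A reader might also infer that the rule hides revisions done elsewhere and that changing the date would bring them to light. The documents do not show that such revisions explain non-return, and last-contact censoring would miss them too. That is informative loss, a separate problem.

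This should be fixed, but it does not undermine the analysis.

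**What to change.** Replace the sentence in SAP 6.4, and align the discontinuation clause in 6.9.1, along these lines:

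*Subjects lost to follow-up or withdrawn are censored at the last date on which the implant was documented as unrevised, whether at a clinic visit, a telephone assessment or a consented family doctor/GP contact. Deaths are censored at the date of death if implant status up to death is known, and otherwise at that last date.*

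The cost is one derived date. The case report form is not among the documents, and Protocol 16.0 has family doctor contacts recorded in source documentation, so the sponsor should check that revision status and its date are captured from those contacts and from the telephone calls. The estimate may be slightly lower and its interval wider. No visit, treatment or sample size changes. The change does not remove bias from informative loss; the numbers lost and the last-known-status dates should be reported beside the curve.
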